### **Investigational Drugs:**

- Group 1. Dapagliflozin 10 mg once daily (n=196)
- Group 2. Placebo once daily (n=196)

### **Treatment Protocol:**

Patients admitted with exacerbation of chronic heart failure by clinical and radiologic features will be considered as candidates for participation. Patients will be approached and invited to participate during the hospital admission. Patients that fulfill inclusion/exclusion criteria will undergo baseline testing and will be randomized prior to discharge will be randomized 1:1 to receive either dapagliflozin 10 mg/day or matching placebo at the time of discharge.

**Inpatient Heart failure treatment.** Patients will receive standard treatment for ADHF by their primary care team and/or cardiology service including diet and pharmacological treatment with diuretics, ACE-I/ARBs, ARNI, beta receptor antagonists, aldosterone antagonists, hydralazine/nitrate combination following the ACCF/AHA Guidelines for the Management of Heart Failure .

**Inpatient T2D Treatment.** Patients with T2D will be treated with a standard insulin regimen during the hospital stay . Prior to hospital discharge, patients will be randomized 1:1 to either dapagliflozin or placebo. All patients will receive diabetes education. The day of discharge, dapagliflozin /matching placebo will be added to the subject's pre-admission treatment regimen.

**Hospital Heart Failure Education.** Hospital discharge HF education will be conducted by the Advanced Practice Providers. They will provide comprehensive education on HF, diet, symptoms, and medications.

**Hospital T2D Education.** Prior to discharge, all patients with T2D will receive information on:

[figure not shown]
1. Diabetes education, if not received within 1 year of admission.
2. Blood glucose target between 80 and 180 mg/d before meals.
3. Use of glucose meters for home glucose self-monitoring.
4. Measurement of urinary ketones.
5. Keeping BG records. Participants will receive a logbook to record glucose tests results.
6. Hypoglycemia recognition and management.
7. Insulin administration (if needed).
8. Education about signs and symptoms of diabetic ketoacidosis, use of glucose monitoring and urinary ketone testing.

### Treatment recommendations at discharge in patients with diabetes

**Study Medications:** Study subjects will be randomized 1:1 to receive either dapagliflozin 10 mg or matching placebo at the time of discharge.

#### Admission HbA1c between 6.5% and 8%:

- Start study medication (dapagliflozin or placebo) once daily
- If no contraindications, re-start OADs (metformin, DPP4-i) at the same dose prior to admission
- Hold sulfonylureas or insulin secretagogues if HbA1c < 7.0%. If HbA1c >7%, reduce dose of sulfonylurea and insulin secretagogues by 50% or stopped according to physician discretion.
- In patients receiving insulin prior to admission, reduce TDD of hospital dose by 50% .

#### Admission HbA1c between 8% and 10%:

- **Patients receiving OAD treatment prior to admission:**
  - Start study medication (dapagliflozin or placebo) once daily
  - If no contraindications, re-start OADs prior to admission (metformin, DPP-4 inhibitors)
  - Hold sulfonylureas or insulin secretagogues if HbA1c < 8.0%. If HbA1c >8%, reduce dose of sulfonylurea and insulin secretagogues by 50% or stopped according to physician discretion.
- **Patients receiving OAD and insulin combination prior to admission:**
  - Start study medication (dapagliflozin or placebo) once daily
  - If no contraindications, re-start OADs prior to admission, except for sulfonylureas, insulin secretagogues or thiazolidinedione (as described above).
  - Discharge patient on basal insulin at 50% of daily hospital dose.
- **Patients receiving basal bolus insulin treatment prior to admission:**

- Start study medication (dapagliflozin or placebo) once daily
- Discharge on basal insulin at 50% of hospital dose or 75% of pre-admission daily insulin dose.

#### Admission HbA1c > 10%:

- **Patients receiving OAD treatment prior to admission:**
  - Start study medication (dapagliflozin or placebo) once daily
  - If no contraindications, re-start OADs prior to admission (metformin, DPP-4 inhibitors)
  - If HbA1c >10%, reduce dose of sulfonylurea and insulin secretagogues by 50%.
  - Insulin naïve patients prior to admission, reduce TDD of hospital insulin dose by 25%.
- **Patients receiving OAD and insulin combination prior to admission:**
  - Start study medication (dapagliflozin or placebo) once daily
  - If no contraindications, re-start OADs prior to admission, except for sulfonylureas, insulin secretagogues or thiazolidinedione.
  - In patients receiving insulin prior to admission, reduce TDD of hospital dose by 25%.
- **Patients receiving basal bolus insulin treatment prior to admission:**
  - Start study medication (dapagliflozin or placebo) once daily
  - Discharge on basal insulin at 50% of hospital dose or 75% of pre-admission daily insulin dose.

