## **Rescue therapy**

Patients with T2D will be discharge on pre-admission oral agents and or insulin therapy except for sulfonylureas or TZDs. Dose of OADs and/or insulin will be adjusted as an outpatient to achieve and maintain a fasting BG between 80-140 mg/dl and a random BG < 180 mg/dl.

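### The discharge-insulin instructions conflict between sections, leave an open choice for basal-bolus patients, and give eligible T2D patients with HbA1c below 6.5% no tier

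*Combined protocol and SAP*

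**What the plan says.** Two general statements cover discharge in T2D. Treatment Protocol (Inpatient T2D Treatment) says: "The day of discharge, dapagliflozin /matching placebo will be added to the subject's pre-admission treatment regimen". Rescue therapy says: "Patients with T2D will be discharge on pre-admission oral agents and or insulin therapy except for sulfonylureas or TZDs". Its only exceptions are those two drug classes, and it goes on to outpatient adjustment towards glucose targets.

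The tiers under Treatment recommendations at discharge in patients with diabetes set insulin for prior users differently:

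- **HbA1c 6.5% to 8%:** "In patients receiving insulin prior to admission, reduce TDD of hospital dose by 50" percent.
- **HbA1c 8% to 10%, oral agents plus insulin:** "Discharge patient on basal insulin at 50% of daily hospital dose".
- **HbA1c 8% to 10%, basal-bolus:** half the hospital dose, or three quarters of the pre-admission dose.
- **HbA1c above 10%, oral agents plus insulin:** "In patients receiving insulin prior to admission, reduce TDD of hospital dose by 25" percent.
- **HbA1c above 10%, basal-bolus:** "Discharge on basal insulin at 50% of hospital dose or 75% of pre-admission daily insulin dose".

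The lowest tier is headed "Admission HbA1c between 6.5% and 8" percent. The Patients section admits T2D patients on pre-admission insulin up to 0.4 unit/kg/day, and the inclusion and exclusion criteria set no HbA1c minimum.

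**The concern.** Neither general statement refers to the tiers, the tiers do not say that they override the general statements, and no order of precedence is given. A site that follows Rescue therapy and a site that follows the tier for the patient's HbA1c can both be following the protocol and still send similar patients home on different starting insulin. Within the tiers, the basal-bolus branch names two doses calculated from different bases and does not say when each applies.

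The starting dose is the background to which blinded study drug is added. Safety Variables lists ketoacidosis and hypoglycemic events as being of special interest. Hypoglycemia risk protection expects hypoglycemia in about 20% to 30% of subjects on basal insulin plus study drug. The first scheduled contact after discharge is at week 2. Change in HbA1c is a secondary outcome in T2D patients, so differences between sites in starting insulin also add noise there.

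**Working it through.** The plan states no figure to reproduce here. The check sets the rules side by side and then asks how far apart they can be.

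**Which rules reach which patient on insulin before admission**

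| Patient | General statements | Tier rule(s) | Candidate rules |
|---|---|---|---|
| HbA1c below 6.5% | pre-admission therapy | none | 1 |
| 6.5% to 8%, any insulin | pre-admission therapy | 50% of hospital | 2 |
| 8% to 10%, oral agents + basal-bolus, both headings | pre-admission therapy | 50% of hospital; 75% of pre-admission | 3 |
| above 10%, oral agents + basal insulin | pre-admission therapy | 75% of hospital | 2 |
| above 10%, basal-bolus only | pre-admission therapy | 50% of hospital; 75% of pre-admission | 3 |
| above 10%, oral agents + basal-bolus, both headings | pre-admission therapy | 75% of hospital; 50% of hospital; 75% of pre-admission | 4 |

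**Exactly 8%.** This value belongs to the first and second tiers. For oral agents plus insulin both give 50% of the hospital dose, so the overlap changes nothing. For basal-bolus patients the second tier adds the 75% of pre-admission alternative.

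**Size of the disagreement.** Let P be the pre-admission total daily dose and H the hospital total daily dose. P is set at 0.4 unit/kg, the limit in the Patients section. H is not in the documents and is assumed to lie between 0.5P and 2P. The general statements are represented by P, which is an inference because they do not name a dose. The candidates are P, 0.50H, 0.75H and 0.75P, in unit/kg/day:

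| H/P | P | 0.50H | 0.75H | 0.75P | Largest/smallest, all four | Same, without 0.75H | 0.50H against 0.75P only |
|---|---|---|---|---|---|---|---|
| 0.5 | 0.40 | 0.10 | 0.15 | 0.30 | 0.40/0.10 = 4.0 | 4.0 | 0.30/0.10 = 3.0 |
| 1.0 | 0.40 | 0.20 | 0.30 | 0.30 | 0.40/0.20 = 2.0 | 2.0 | 0.30/0.20 = 1.5 |
| 1.5 | 0.40 | 0.30 | 0.45 | 0.30 | 0.45/0.30 = 1.5 | 0.40/0.30 = 1.33 | 1.0 |
| 2.0 | 0.40 | 0.40 | 0.60 | 0.30 | 0.60/0.30 = 2.0 | 0.40/0.30 = 1.33 | 0.40/0.30 = 1.33 |

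The ratios depend only on H/P, not on the choice of P. The last column isolates the unresolved choice in the basal-bolus branch. It needs neither the general statements nor any view on whether the headings overlap, and the two options coincide only at H = 1.5P.

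**The case against.** The strongest reply is that the tiers are the specific discharge section and the two general statements only sketch the approach, so a careful reader would follow the tiers. The three headings in the upper tiers can also be read as oral agents only, oral agents plus insulin, and insulin only, because the basal-bolus branch gives no instruction about oral agents. Both readings are reasonable. They are not written down, however, and even if both are adopted the choice inside the basal-bolus branch and the gap below 6.5% remain.

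Several stronger conclusions that a reader might draw are not supported:

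- **That all four rules meet in any patient.** They meet only above 10%, on oral agents plus basal-bolus insulin, and only if both headings apply. With exclusive headings, at most three meet.
- **That the general statements order an unchanged dose.** They name the pre-admission regimen or therapy. For oral agents the lowest tier does specify the same dose; nothing equivalent is said for insulin.
- **That patients below 6.5% get no reduction, or relatively more insulin than the tier above.** The tiers are silent about them. The post-discharge titration table, Rescue therapy and Hypoglycemia risk protection allow later changes at any HbA1c. The halving at 6.5% to 8% is taken from the hospital dose, and at H = 2P it returns exactly the pre-admission dose.
- **That a discharge dose above 0.4 unit/kg breaches eligibility.** That limit applies before admission only.
- **That the arms are biased.** Randomization is double-blind and in blocks by diabetes status, so variation in starting insulin falls on both arms alike in expectation.

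**Conclusion.** The point stands as an internal contradiction about starting insulin. The general statements and the tiers disagree with no stated precedence, the basal-bolus choice has no criterion, the branches are not declared exclusive, exactly 8% sits in two tiers (which matters for basal-bolus patients only), and eligible patients below 6.5% have no discharge adjustment specified beyond the general statements.

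In the patient type where all four rules can meet, the candidates differ about 1.5- to 4-fold. This rests on the assumed hospital dose of 0.5 to 2 times pre-admission, on both headings applying, and on reading the general statements as the pre-admission dose. With exclusive headings the range for a basal-bolus patient is about 1.33- to 4-fold. How many patients would be affected cannot be estimated from the documents.

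The consequence is for patient safety and site-to-site variability. The validity of the primary comparison is not in question.

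**What to change.** Reconcile Treatment Protocol, Rescue therapy and the three HbA1c tiers so that one set of discharge-insulin instructions governs and the other sections refer to it. In that set, state:

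1. how the regimen branches are to be applied, including to a patient on oral agents plus basal-bolus insulin;
2. how the choice in the basal-bolus branch is to be made;
3. which single tier holds HbA1c of exactly 8%;
4. which instruction covers T2D patients with HbA1c below 6.5%.

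The sponsor decides the clinical content; no dose is proposed here. Measurements During follow-up already records insulin dosage, so at most check that the pre-admission, hospital and discharge total daily doses are each captured. The cost is protocol wording and perhaps one line on the case report form, with no added patients or visits.

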#### Algorithm for basal insulin dose adjustment after hospital discharge:

Basal Insulin	
If mean FBG > 180 mg/dL for the last 2 consecutive days and no episodes of hypoglycemia (BG <70 mg/dL)	Increase TDD by 4 IU
If mean FBG > 140 mg/dL for the last 2 consecutive days and no episodes of hypoglycemia (BG <70 mg/dL)	Increase TDD by 2 IU
If mean FBG between 100 to 140 mg/dL for the last 2 days and no hypoglycemia	No Change
If any FBG between 70 – 99 mg/dl	Decrease by 4 IU or 10% of TDD
If any FBG or RBG < 70 mg/dl	Decrease by 8 IU or 20% of TDD
If any FBG or RBG < 40 mg/dl	Decrease TDD by 30%

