### **Hypoglycemia risk protection:**

We will follow safeguards to minimize the risk to our subjects: a) we will carefully monitor response to medical treatment every 2 weeks by telephone contact and during clinic visits, b) women of reproductive age who are sexually active will undergo a urine pregnancy tests prior to participation in the study, c) patients with significant comorbidities such as chronic kidney disease greater than stage II, cirrhosis, gastroparesis, and pancreatic disease will be excluded from the study.

**Hypoglycemia:** We expect that less than 10% of dapagliflozin treated patients will experience hypoglycemia during follow-up; however, approximately 20% to 30% of subjects treated with basal insulin and study drug will experience one or more episodes of hypoglycemia. Patients will receive diabetes education prior to discharge and will be instructed on hypoglycemia sign/symptoms and

treatment. Patients will be asked to call the T2D center and/or PCP in the event of hypoglycemia. If a patient develops hypoglycemia, the daily dose of insulin will be reduced by 10% to 30%.

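### The post-discharge basal-insulin table can order opposite dose changes on the same readings, and it disagrees with the protocol's own glucose target and stated range of insulin reductions

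*Combined protocol and SAP*

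**What the plan says.** The table under Algorithm for basal insulin dose adjustment after hospital discharge has six rows.

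- **Increases.** A two-day mean fasting glucose (FBG) above 180 mg/dL gives "Increase TDD by 4 IU"; a mean above 140 gives "Increase TDD by 2 IU". Both rows carry the condition "for the last 2 consecutive days and no episodes of hypoglycemia (BG <70 mg/dL").
- **No change.** A two-day mean FBG of 100 to 140 without hypoglycemia.
- **Decreases.** Any single FBG of 70–99 gives "Decrease by 4 IU or 10% of TDD". Any fasting or random value below 70 gives "Decrease by 8 IU or 20% of TDD". Any value below 40 gives "Decrease TDD by 30"%.

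Three other places bear on the same decisions. Rescue therapy says that treatment is adjusted to achieve and "maintain a fasting BG between 80-140 mg/dl and a random BG < 180 mg/dl". Hospital T2D Education, under Treatment Protocol, teaches patients a pre-meal target of 80 to 180. Hypoglycemia risk protection says that after hypoglycemia "the daily dose of insulin will be reduced by 10% to 30"%.

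**The concern.** Increases are judged on a mean and decreases on a single value, so one pair of readings can satisfy both, and nothing says which row governs. The table also reduces insulin at values that Rescue therapy names as the goal. Finally, two of the three decrease rows offer a fixed and a proportional cut that diverge as the dose moves away from one point, with no rule for choosing.

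At stake is a safety-relevant dose in insulin-treated patients. Hypoglycemia and ketoacidosis are events of special interest under Safety Variables. Change in HbA1c in patients with type 2 diabetes is a secondary outcome, and inconsistent titration may add variation to it.

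**Working it through.** The plan states no figure to reproduce here. The check applies the table's rows to readings and doses.

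**1. Rows met by pairs of fasting readings (mg/dL).** Inputs: the table's thresholds. Formula: mean = (first + second)/2.

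| Readings | Mean | Rows met |
|---|---|---|
| 95, 200 | 147.5 | +2 IU; and −4 IU or −10% |
| 90, 280 | 185 | +4 IU; +2 IU; and −4 IU or −10% |
| 85, 130 | 107.5 | no change; and −4 IU or −10% |
| 82, 90 | 86 | −4 IU or −10% only |

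No reading is below 70, so the hypoglycemia condition does not block the increase or no-change rows.

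**2. Table against targets.** In the last line both readings are inside 80–140 (Rescue therapy) and inside 80–180 (Hospital T2D Education), yet the table orders a cut. The overlap between target and decrease row is 80–99. At the upper end the two targets differ from each other, 140 against 180; the table follows 140.

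**3. Fixed against proportional cuts.** The options agree where 8 = 0.20 × TDD, so TDD = 40 IU, and where 4 = 0.10 × TDD, again 40 IU. The 8 IU option exceeds the 30% set for a value below 40 when 8 > 0.30 × TDD, that is TDD < 8/0.30 = 26.7 IU. The same threshold takes the 8 IU option above the 30% upper limit in Hypoglycemia risk protection.

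| TDD (IU, illustrative) | 8 IU as % of TDD | 20% of TDD (IU) | 30% of TDD (IU) |
|---|---|---|---|
| 16 | 50% | 3.2 | 4.8 |
| 20 | 40% | 4.0 | 6.0 |
| 24 | 33.3% | 4.8 | 7.2 |
| 30 | 26.7% | 6.0 | 9.0 |
| 40 | 20% | 8.0 | 12.0 |

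At 16 IU the two options for a value below 70 differ by 8/3.2 = 2.5-fold. From 30 IU upward in this table, the 8 IU cut is below the 30% cut.

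**4. How many patients are below 26.7 IU?** The documents give an eligibility cap of 0.4 unit/kg/day on the pre-admission dose (Patients), but no weights, no dose distribution and no cap on the hospital dose. At the cap, TDD is below 26.7 IU under 26.7/0.4 = 66.7 kg on the full dose, and under 66.7/0.75 = 88.9 kg on 75% of it.

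The shares below were simulated under these assumptions:
- mean weight 80–100 kg (SD 18–22);
- pre-admission dose uniform over 0.1–0.4, 0.2–0.4 or 0.3–0.4 U/kg, or fixed at the cap;
- hospital dose 0.3–0.6 U/kg.

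| Discharge dose | Share below 26.7 IU |
|---|---|
| Full pre-admission dose | 6–78% |
| 75% of pre-admission dose | 31–96% |
| 50% of hospital dose | 31–100% |
| 75% of hospital dose | 3–98% |

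The ranges are too wide to support any statement about a majority.

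**The case against.** The best defence is that the rows are meant as tiers. A mean above 180 also satisfies the above-140 row, and a value below 40 also satisfies the below-70 row; a clinician would take the more extreme row in each pair. That settles those two overlaps. It does not settle an increase against a decrease, because one rule reads the mean and the other a single value.

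A no-change band of 100–140 inside a wider target of 80–140 could be a deliberate buffer. If so, the protocol does not say so, and the text still both aims for 80–99 and cuts insulin there. The 141–180 discrepancy is a weaker point against the table: it lies mainly between the patient-education target and the other two sections.

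The inversion between the below-70 and below-40 rows is conditional. It needs the 8 IU option, a TDD below 26.7 IU, and the below-40 row read as replacing the below-70 row. The 20% option in the same cell is always less than 30%, and the table's percentages all sit within 10% to 30%. All of this stands, and the point is limited accordingly.

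A reader might infer from the 0.4 unit/kg cap that most insulin users are affected. The documents do not support that. The cap applies to the pre-admission dose, while the discharge rules mostly scale an uncapped hospital dose, by 50% in some branches and 25% in others. At the cap an 80 kg patient takes 0.4 × 80 = 32 IU, which is above the threshold.

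**Conclusion.** The inconsistency is real and should be corrected. Two parts follow from the text alone: rows that conflict on the same readings with no precedence, and a decrease triggered at 80–99 inside the fasting target. The third is conditional: with the 8 IU option and a TDD below about 27 IU, the cut for glucose below 70 is larger than the 30% cut for glucose below 40 and falls outside the stated 10% to 30% range. The number of patients in that dose range cannot be determined.

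The consequence is that staff following the table literally may reach different or opposite dose changes, with possible added noise in HbA1c among insulin-treated patients. A reader might also infer bias between the arms or an effect on the primary heart-failure composite. The documents show neither: the trial is double-blind and randomization is blocked by diabetes status.

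**What to change.** Reconcile four places: the basal-insulin table, Rescue therapy, Hospital T2D Education and Hypoglycemia risk protection. After the revision:

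- no set of readings should meet conflicting rows;
- the way to choose between the IU and the percentage option should be stated;
- the fasting target and the range of insulin reductions should agree wherever they appear, or any intended difference should be explained.

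The sponsor sets all values and rules; this review takes no view on which is right. The cost is one rewritten table and a few sentences, with no added patients or procedures.

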#### Schedule of Clinic and Phone Visits:

The study will include 10 study contacts: 1 screening visit and 1 randomization visit while subjects are still in the hospital. After discharge, patients will have a total of 5 in-person clinic visits and 3 phone contacts over a 26-week period.

At the Screening Visit, patients will be evaluated for participation using inclusion and exclusion criteria. At Visit 1 - Randomization, subjects will be randomized to receive the study drug that will commence after discharge and will be added to the ongoing therapy. The study treatment period will end at Visit 9 (week 26). The following table provides information as to the study procedures to be completed at each visit.

**Schedule of Assessments:**

Visit		2	3	4	5	6	7	8	9
Screening	Randomization (Discharge) c								
Week	0	0	2	6	8	12	16	20	24
Clinic / CTSA Visit		X	X	X		X		X	X
Phone Visit					X		X		X
Sign Informed Consent	X								
Medical History	X								
Weight, BMI	X	X		X		X		X	X
Physical Exam	X	X		X		X		X	X
Vital Signs	X	X		X		X		X	X
Blood & Urine Sampling a	X	X		X ^		X		X ^	X
Urine Pregnancy Test b	X			X		X		X	X
6-minute Walk Distance			X			X			X
KCCQ Questionnaire		X				X			X
CHQ-SAS Questionnaire		X				X			X
AEs and SAEs		X	X	X	X	X	X	X	X
Electrocardiogram		X d							
Echocardiogram c		X				X			
Review Home BG Testing Results in T2D			X	X	X	X		X	X
Home Urine Ketone Testing, if Indicated			X	X	X	X		X	X
Study Drug Dispensing		X				X			
Study Drug Returned						X			X
T2D Education	X								
Heart Failure Education	X								

aAdmission tests: For screening purposes we will use available laboratory results during current admission (chemistry including eGFR, HbA1c, urine studies), additional testing will be necessary to meet all the baseline lab requirements such as serum magnesium, NT-proBNP, ketones (patients with T2D at investigator's discretion), albumin/creatinine ratio, random urine sodium , at baseline (prior to discharge). Follow up testing at 12 and 26 weeks; other ^blood tests at 6 and 20 weeks and urine culture will be performed at investigator's discretion. bUrine pregnancy test for women with childbearing potential at investigator's discretion c Echocardiogram during hospital admission (or within 6 months prior to index hospitalization) and at 12 weeks follow up visit. All visits have a +/-7-day visit window. d the most current ECG during admission. e Randomization can be performed prior to discharge or up to 7 days after discharge (if discharge planning over the weekend. \*\*COVID-19: For modified study visit options applicable during the time period of the COVID-19 emergency, please see appendix B.

